5.3.2 Vital Signs

Vital signs evaluations will be performed at visits as shown in the Flow Chart. This includes systolic/diastolic blood pressure, pulse rate, temperature, and respiratory rate. Blood pressure, pulse rate, and respiratory rate will be measured after patients have been sitting comfortably for at least five minutes. Measurement of vital signs should precede blood sampling to avoid the impact of blood sampling on the vital measurements. At dosing visits vital signs

evaluations will be performed pre-dose and at Visit 2 and Visit 3 additional evaluations will be taken at approximately 5 minutes post-dose (5 minutes after last injection) and approximately 60 minutes post-dose (60 minutes after last injection).

Patients should be closely monitored for signs and symptoms of hypersensitivity reactions for approximately 2 hours after the last injection at Visit 2 and for approximately 1 hour after the last injection at all other visits with drug administration. Hypersensitivity reactions should be treated according to medical standards. Pre-medications for further injections might be considered and will be agreed on between investigator and BI clinical monitor.

5.3.3 Safety laboratory parameters

The laboratory tests listed in Table 5.3.3: 1 will be performed by the central laboratory service provider. A local laboratory may be used for selected tests in exceptional cases. Patients should be fasting for at least 8 hours prior to the blood sample being taken (except screening visit).

Instructions regarding sample collection, sample handling/processing, and sample shipping are provided in the Laboratory Manual in the ISF. For time points of laboratory sampling, see [Flow Chart](#).

Laboratory results (i.e., all safety laboratory and clinical laboratory data relevant for current clinical practice) of the patients will be available in real time to the respective investigator (via laboratory reports) and to the sponsor (via the central laboratory website) and selected abnormal laboratory alerts will be flagged to the site and sent to sponsor in real time.

Clinically relevant abnormal findings will be reported as baseline conditions or AE's. A clinically relevant value may be either in or outside the reference range. Clinically relevant abnormal laboratory test results must be confirmed using an unscheduled visit laboratory kit and should be repeated until normalisation or stabilisation or until an alternative explanation has been found. Abnormal laboratory values will be also graded for intensity by using RCTC Version 2.0 criteria ([R13-3515](#)).

Table 5.3.3: 1 Laboratory tests

Category	Test name
Haematology	Hematocrit Hemoglobin (Hb) Glycosylated Hbc (HbA1c) Red Blood Cell Count/Erythrocytes Reticulocyte Count White Blood Cells/Leukocytes Platelet Count/Thrombocytes
Differential Automatic	Neutrophils (relative and absolute count) Eosinophils (relative and absolute count) Basophils (relative and absolute count) Monocytes (relative and absolute count) Lymphocytes (relative and absolute count)

Table 5.3.3: 1 (continued)

Laboratory tests

Category	Test name
Differential Manual (if Differential Automatic is abnormal)	Neutrophils, bands (Stabs) Neutrophils, polymorphonuclear (PMN) Eosinophils Basophils Monocytes Lymphocytes
Coagulation	Activated Partial Thromboplastin Time (aPTT) Prothrombin time (INR) Fibrinogen
Enzymes	AST(GOT) ALT(GPT) Alkaline Phosphatase (AP) Creatine Kinase (CK) CK-MB, only if CK is elevated Gamma-Glutamyl Transferase (GGT/γ-GT) Lactic Dehydrogenase (LDH) Amylase Lipase
Electrolytes	Calcium Sodium Potassium Chloride Bicarbonate
Substrates	Glucose BUN Uric acid Creatinine eGFR (estimated by CKD-EPI formula) Bilirubin Total Bilirubin Direct (if total is elevated) Bilirubin Indirect (if total is elevated) Troponin (reflex, in case of elevated CK) Albumin C-Reactive Protein (CRP) (high sensitivity) Cholesterol, total Triglycerides LDL-Cholesterol HDL-Cholesterol
Urine Pregnancy test (only for female patients of childbearing potential; test done in clinic)	Human Chorionic Gonadotropin in the urine
Serum Pregnancy test (only for female patients of childbearing potential at screening or if urine pregnancy test is positive)	Human Serum Chorionic Gonadotropin
Hormones (only at screening)	TSH, (free T3 and T4 in case of abnormal TSH)
Autoantibodies (only at screening)	Rheumatoid Factor

Table 5.3.3: 1 (continued)

Laboratory tests

Category	Test name
Urinalysis (dipstick)	Urine Nitrite Urine Protein Urine Glucose Urine Ketone Urobilinogen Urine Bilirubin Urine RBC/Erythrocytes Urine WBC/Leukocytes Urine pH
Urine-Sediment (microscopic examination, only if urine analysis abnormal)	Urine Sediment Bacteria Urine Cast in Sediment Urine Squamous Epithelial Cells Urine Sed. Crys., Unspecified Urine Sediment RBC/Erythrocytes Urine Sediment WBC/Leucocytes
Urine	Albumin (quantitative) Creatinine Albumin/creatinine ratio
Infection screening	Hepatitis B Surface Antigen (qualitative) ¹ Hepatitis B Surface Antibody (qualitative) ¹ Hepatitis B Core Antibodies total (qualitative) ¹ Hepatitis B Virus DNA (quantitative) ^{1,2} Hepatitis C Antibodies (qualitative) ¹ HIV-1, and HIV-2 Antibody (qualitative) ^{1,2} QuantiFERON®-TB ³ (if applicable)

¹ Hepatitis B, hepatitis C and HIV testing will be performed at screening and FU2/EOO Visit.

² If Hepatitis B Surface Antigen is negative but Hepatitis B Core Antibodies total is positive and/or Hepatitis B Surface Antibody is positive, Hepatitis B Virus DNA will be quantified. If HBV DNA level is undetectable (<20 IU/mL) at screening, the patient can participate in this trial. However, HBV DNA level will be monitored at least every 6 months.

³ TB testing will be performed at screening and FU2/EOO Visit. QuantiFERON®, T-SPOT® or PPD skin test may be performed. T-SPOT® and PPD skin test will be performed at local laboratory.

5.3.4 **Electrocardiogram**

The 12-lead ECGs will be performed as scheduled in the [Flow Chart](#).

ECGs will be recorded after the patients have rested for at least 5 minutes in a supine position and will always precede blood sampling. Six limb leads, as specified by Einthoven (I, II and III) and Goldberger (aVR, aVL, aVF), and six pre-cordial leads (V1–V6), according to Wilson, will be used.

ECGs may be repeated for quality reasons and the repeat used for analysis. Additional ECGs may be collected for safety reasons. Clinically relevant, abnormal findings will be reported as AEs.

Information about the details of ECG collection and the parameters assessed will be provided in the ISF.

ECGs will be read and evaluated by a central vendor. The study site will be informed about the results of the assessment of the ECG obtained at screening and if there are findings which would exclude the patient from study participation according to exclusion criterion in [Section 3.3.3.](#)

The electronic version of the ECG is regarded as source data.

5.3.5 Other safety parameters

Local tolerability at the administration site of the subcutaneous injection will be assessed by the investigator according to “swelling”, “induration”, “heat”, “redness”, “pain”, or “other findings” at the specified visits as noted in the [Flow Chart](#). This assessment should be done pre-dose.

5.3.6 Assessment of adverse events

5.3.6.1 Definitions of AEs

Adverse event

An adverse event (AE) is defined as any untoward medical occurrence in a patient or clinical investigation subject administered a medicinal product and which does not necessarily have to have a causal relationship with this treatment.

An AE can therefore be any unfavourable and unintended sign (including an abnormal laboratory finding), symptom, or disease temporally associated with the use of a medicinal product, whether or not considered related to the medicinal product.

Adverse reaction

An adverse reaction is defined as a response to a medicinal product which is noxious and unintended. Response in this context means that a causal relationship between a medicinal product and an AE is at least a reasonable possibility. Adverse reactions may arise from use of the product within or outside the terms of the marketing authorisation or from occupational exposure. Conditions of use outside the marketing authorisation include off-label use, overdose, misuse, abuse, and medication errors.

Serious adverse event

A serious adverse event (SAE) is defined as any AE which:

- results in death,
- is life-threatening, this refers to an event in which the patient was at risk of death at the time of the event; it does not refer to an event that hypothetically might have caused death if more severe.
- requires inpatient hospitalisation or
- prolongation of existing hospitalisation,
- results in persistent or significant disability or incapacity, or
- is a congenital anomaly/birth defect, or

Proprietary confidential information © 2017 Boehringer Ingelheim International GmbH or one or more of its affiliated companies

- is to be deemed serious for any other reason if it is an important medical event when based upon appropriate medical judgment which may jeopardise the patient and may require medical or surgical intervention to prevent one of the other outcomes listed in the above definitions.

Medical and scientific judgement should be exercised in deciding whether other situations should be considered serious reactions, such as important medical events that might not be immediately life threatening or result in death or hospitalisation but might jeopardise the patient or might require intervention to prevent one of the other outcomes listed above.

Examples of such events are intensive treatment in an emergency room or at home for allergic bronchospasm, blood dyscrasias, or convulsions that do not result in hospitalisation or development of dependency or abuse. Any suspected transmission via a medicinal product of an infectious agent is also considered a serious adverse reaction.

The following events will be handled as “deemed serious for any other reason”. An AE which possibly leads to disability will be reported as an SAE.

AEs considered “Always Serious”

Cancers of new histology and exacerbations of existing cancer must be reported as a serious event regardless of the duration between discontinuation of the drug and the occurrence of the cancer.

In accordance with the European Medicines Agency initiative on Important Medical Events, BI has set up a list of further AEs, which by their nature, can always be considered to be “serious” even though they may not have met the criteria of an SAE as given above.

The latest list of “Always Serious AEs” can be found in the EDC-system. These events should always be reported as SAEs as given above.

Adverse events of special interest (AESIs)

The term AESI relates to any specific AE that has been identified at the project level as being of particular concern for prospective safety monitoring and safety assessment within this trial, e.g., the potential for AEs based on knowledge from other compounds in the same class. AESI need to be reported to the sponsor’s Pharmacovigilance Department within the same timeframe that applies to SAE. Please see above.

The following are considered as AESIs:

Hepatic injury

A hepatic injury is defined by the following alterations of hepatic laboratory parameters:

- an elevation of AST and/or ALT ≥ 3 fold ULN combined with an elevation of total bilirubin ≥ 2 fold ULN measured in the same blood draw sample, and/or
- marked peak aminotransferase (ALT, and/or AST) elevations ≥ 10 fold ULN

These lab findings constitute a hepatic injury alert and the patients showing these lab abnormalities need to be followed up according to the “DILI checklist” provided in the ISF.

In case of clinical symptoms of hepatic injury (icterus, unexplained encephalopathy, unexplained coagulopathy, right upper quadrant abdominal pain, etc.) without lab results (ALT, AST, total bilirubin) available, the investigator should make sure these parameters are analysed, if necessary in an unscheduled blood test. Should the results meet the criteria of hepatic injury alert, the procedures described in the DILI checklist should be followed.

Intensity of AEs

The intensity grading of AEs will be performed according to Rheumatology Common Toxicity Criteria (RCTC) Version 2.0 developed by OMERACT ([R13-3515](#)). Refer to ISF for intensity/severity classification. Intensity options are:

Grade 1	mild
Grade 2	moderate
Grade 3	severe
Grade 4	life –threatening

Causal relationship of AEs

The definition of an adverse reaction implies at least a reasonable possibility of a causal relationship between a suspected medicinal product and an AE. An adverse reaction, in contrast to an AE, is characterised by the fact that a causal relationship between a medicinal product and an occurrence is suspected.

Medical judgment should be used to determine the relationship, considering all relevant factors, including pattern of reaction, temporal relationship, de-challenge or re-challenge, confounding factors such as concomitant medication, concomitant diseases and relevant history.

Arguments that may suggest that there is a reasonable possibility of a causal relationship could be:

- The event is consistent with the known pharmacology of the drug
- The event is known to be caused by or attributed to the drug class.
- A plausible time to onset of the event relative to the time of drug exposure.
- Evidence that the event is reproducible when the drug is re-introduced
- No medically sound alternative etiologies that could explain the event (e.g., preexisting or concomitant diseases, or co-medications).
- The event is typically drug-related and infrequent in the general population not exposed to drugs (e.g. Stevens-Johnson syndrome).
- An indication of dose-response (i.e., greater effect size if the dose is increased, smaller effect size if dose is diminished).

Arguments that may suggest that there is no reasonable possibility of a causal relationship could be:

- No plausible time to onset of the event relative to the time of drug exposure is evident (e.g., pre-treatment cases, diagnosis of cancer or chronic disease within days/weeks of drug administration; an allergic reaction week after discontinuation of the drug concerned)
- Continuation of the event despite the withdrawal of the medication, taking into account the pharmacological properties of the compound (e.g., after 5 half-lives).

Proprietary confidential information © 2017 Boehringer Ingelheim International GmbH or one or more of its affiliated companies

Of note, this criterion may not be applicable to events whose time course is prolonged despite removing the original trigger.

- Additional arguments amongst those stated before, like alternative explanation (e.g. situations where other drugs or underlying diseases appear to provide a more likely explanation for the observed event than the drug concerned).
- Disappearance of the event even though the study drug treatment continues or remains unchanged.

5.3.6.2 Adverse event collection and reporting

AE Collection

[figure not shown]
The Investigator shall maintain and keep detailed records of all AEs in their patient files. The following must be collected and documented on the appropriate CRF by the investigator:

- From signing the informed consent onwards through the residual effect period (REP) until individual patient's end of trial:
 - all AEs (serious and non-serious) and all AESIs.

However, if an individual patient discontinues trial medication prematurely but stays in the trial (i.e., if further visits including telephone visits, or vital status assessments are planned) from then on and until the individual patient's end of the trial the investigator must report related SAEs and related AESIs

- After the individual patient's end of trial:

The investigator does not need to actively monitor the patient for AEs but should only report relevant SAEs and relevant AESIs of which the investigator may become aware of.

The REP is defined as 15 weeks after the last trial medication application. All AEs which occurred through the treatment phase and throughout the REP will be considered as on treatment please see [Section 7.3.4](#). Events which occurred after the REP will be considered as post treatment events.

AE reporting to sponsor and timelines

The investigator must report SAEs, AESIs, and non-serious AEs which are relevant for the reported SAE or AESI, on the BI SAE form via fax immediately (within 24 hours) to the sponsor's unique entry point (country specific contact details will be provided in the ISF). The same timeline applies if follow-up information becomes available. In specific occasions the investigator could inform the sponsor upfront via telephone. This does not replace the requirement to complete and fax the BI SAE form.

All SAEs and AESIs must be reported immediately to the head of the trial site.

With receipt of any further information to these events, a follow-up SAE form has to be provided. For follow-up information the same rules and timeline apply as for initial information.

Information required

For each AE, the Investigator should provide the information requested on the appropriate CRF pages and the BI SAE form. The Investigator should determine the causal relationship to the trial medication.

The following should also be recorded as an (S)AE in the eCRF and SAE form (if applicable):

- Worsening of the underlying disease or of other pre-existing conditions
- Changes in vital signs, ECG, physical examination and laboratory test results, if they are judged clinically relevant by the investigator.

If such abnormalities already pre-exist prior trial inclusion they will be considered as baseline conditions.

All (S)AEs, including those persisting after individual patient's end of trial must be followed up until they have resolved, have been sufficiently characterised, or no further information can be obtained.

Pregnancy

In the rare case pregnancy may occur in a clinical trial. Once a patient has been enrolled into this clinical trial and has taken trial medication, the investigator must report immediately (within 24 hours) a potential drug exposure during pregnancy (DEDP) to the sponsor's unique entry point (contact details will be provided in the ISF). The Pregnancy Monitoring Form for Clinical Trials (Part A) should be used.

The outcome of the pregnancy associated with the drug exposure during pregnancy must be followed up and reported to the sponsor's unique entry point on the Pregnancy Monitoring Form for Clinical Trials (Part B).

The ISF will contain the Pregnancy Monitoring Form for Clinical Trials (Part A and B).

As pregnancy itself is not to be reported as an AE, in the absence of an accompanying SAE and/or AESI, only the Pregnancy Monitoring Form for Clinical Trials and not the SAE form

is to be completed. If there is an SAE and/or AESI associated with the pregnancy as an SAE form must be completed in addition.

Adverse event(s) due to Medical device failure of trial medication

The investigator must report “Medical device failure” that leads to AEs or is judged as a potential cause for leading SAEs by the investigator, on the Product/Device Complaints Form to the sponsor, see the instruction in ISF. “Medical device failure” that lead to SAEs and/or AESIs or is judged as a potential cause for leading SAE must be reported to the sponsor’s Pharmacovigilance Department immediately.

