For randomised patients leaving the study before the planned end of observation (EOO), their vital status should be collected at Week 56.

For randomised patients the reason for withdrawal (e.g., AEs) must be recorded in the case report form (CRF). These data will be included in the trial database and reported.

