11.2 Analysis of Adverse Events

11.2.1 Treatment-Emergent Adverse Events

Treatment-emergent adverse events (TEAEs) are defined as any event with an onset that is after the first dose of study drug and with an onset date within 105 days after the last dose of study drug in the analysis period, or prior to the first dose in the subsequent period for subjects who entered in to the subsequent period. Events where the onset date is the same as the study drug start date are assumed to be treatment-emergent, unless the adverse event start time is prior to the study drug start time. If an incomplete onset date is collected for an adverse event, the event will be assumed to be treatment-emergent unless there is other evidence that confirms that the event is not treatment-emergent (e.g., the event end date is prior to the study drug start date).

The data cutoff date (December 15, 2017) will be applied to TEAEs during the interim analysis, in accordance to the duration of study drug exposure defined up to this cutoff date.

Summary tables will be presented as follows:

1. Adverse Event Overview

The number and percentage of subjects experiencing treatment-emergent adverse events will be summarized for the following adverse event categories.

- Any AE
- Any AE that was assessed as related to study drug by the investigator
- Any severe AE
- Any serious AE (SAE)

- Any SAE that was assessed as related to study drug by the investigator
- Any AE leading to discontinuation of study drug.
- Any AE leading to death.
- Any deaths
- Areas of Safety Interest

2. Adverse Events by System Organ Class and Preferred Term

TEAEs will be summarized and presented using primary Medical Dictionary for Regulatory Activities (MedDRA) system organ classes (SOCs) and preferred terms (PTs). The SOCs will be presented in alphabetical order, and the PTs will be presented in alphabetical order within each SOC.

Subjects reporting more than one adverse event for a given MedDRA preferred term will be counted only once for that term (most severe incident for the severity tables and most related incident for the relationship tables). Subjects reporting more than one type of adverse event within a SOC will be counted only once for that SOC. Subjects reporting more than one type of adverse event will be counted only once in the overall total.

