Serious infections, TB, fungal and opportunistic infections (including herpes zoster) (continued)	Fungal infections	Fungal infections CMQ (code 80000063)	PTs	N
	Herpes Zoster	Herpes zoster CMQ (code 80000175)	PTs	N
Malignancies	All possible malignancies	Narrow – Malignancies (SMQ 20000090)	PTs	N
	Malignant Tumours	Narrow – Malignant tumours (SMQ 20000194)	PTs	Y
	Non-melanoma skin cancer (NMSC)	Broad – Skin malignant tumours (SMQ 20000204) excluding terms identified by the Melanoma CMQ (code 80000119)	PTs	N
	Malignant Tumours excluding NMSC	'Malignant Tumours excluding NMSC' is identified by the 'Malignant Tumours' search excluding terms identified by the 'Non-melanoma skin cancer (NMSC)' search.	PTs	Y

Table 10. Areas of Safety Interest (Continued)

ASI Grouping	Categories (ASI)	Search Criteria	Terms to Display	Include in AE Overview (Y/N)
Hypersensitivity Reaction	Hypersensitivity	Narrow – Hypersensitivity (SMQ 20000214)	PTs	Y – serious events only
	Anaphylactic Reaction	Narrow – Anaphylactic reaction (SMQ 20000021)	PTs	N
Hepatic Events	Hepatic Events	Broad – Hepatic failure, fibrosis and cirrhosis and other liver damage-related conditions (SMQ 20000013) Broad – Hepatitis, non-infectious (SMQ 20000010) Broad – Cholestasis and jaundice of hepatic origin (SMQ 20000009) Broad – Liver related investigations, signs and symptoms (SMQ 20000008) Narrow – Liver-related coagulation and bleeding disturbances (SMQ 20000015)	PTs	N

Adverse Event per 100 Patient-Years of Exposure

AEs occurring during the entire study will be presented by event rate per 100 patient years. These will be presented for any TEAEs, serious adverse events, Areas of Safety Interest.

AEs per 100 patient-years of exposure is defined as the number of AEs divided by the total exposure in 100 patient-years. Note that one event per preferred term per day per subject will be counted in the calculation of the number of AEs (i.e., a preferred term will not be counted twice on the same day for the same subject). See the calculation method below.

$$100 \times \frac{\text{Number of TEAEs}}{\text{Total Patient Years}}$$

where total patient years is defined as the sum of the study drug exposure (defined as date of last dose – date of first dose + 105 days (5 half-lives)) of all subjects normalized by 365.25, and rounded to one decimal place.

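### Protocol 5.3.6.2 narrows AE reporting once drug is stopped early, yet protocol and SAP still analyse all AEs, and the SAP counts exposure, for 15 weeks after the last dose

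*Protocol*

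**What the plan says.** **Collection.** The default rule in protocol 5.3.6.2 is full CRF collection of AEs and AESIs: "From signing the informed consent onwards through the residual effect period (REP) until individual patient's end of trial". An exception follows for patients who stop drug prematurely but remain in the trial: "from then on and until the individual patient's end of the trial the investigator must report related SAEs and related AESIs". Remaining in the trial is defined widely: "i.e., if further visits including telephone visits, or vital status assessments are planned". Protocol 3.3.4.1 plans such a contact for everyone who leaves early: "For randomised patients leaving the study before the planned end of observation (EOO), their vital status should be collected at Week 56". The exception may therefore reach nearly every early stopper.

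**Analysis.** The same section fixes the residual effect period (REP): "The REP is defined as 15 weeks after the last trial medication application". It then says: "All AEs which occurred through the treatment phase and throughout the REP will be considered as on treatment". Protocol 7.3.4 uses the same window for treatment-emergent AEs. SAP 11.2.1 counts an event "with an onset date within 105 days after the last dose of study drug in the analysis period", or before the first dose of the next period for subjects who enter it. For rates per 100 patient-years, "total patient years is defined as the sum of the study drug exposure", and that exposure is the last dose date minus the first dose date plus 105 days. None of these rules makes an exception for early stoppers.

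**Text that implies full collection.** Protocol 2.3 relies on collecting all AEs in the treatment and observation periods to monitor infection risk. The Flow Chart marks AEs at every visit, and early stoppers are asked to attend the remaining visits. Protocol 3.1 plans AE follow-up 16 weeks after the last dose for patients not entering the extension. Under 6.2.3.1 early stoppers cannot enter it.

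**The concern.** The exception is triggered by stopping drug, not by the end of the REP. Between those two points an early stopper is still analysed as on treatment and still adds person-time, but the only events that must be reported are those the investigator judges related and that are also serious or AESIs. Protocol 5.3.6.1 lists only hepatic injury as an AESI. An unrelated serious infection, a non-serious herpes zoster or fungal infection, or a non-serious cardiovascular event in that interval need not reach the CRF.

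The SAP tabulates any AE, any SAE and the areas of safety interest regardless of causality, so for these patients the input would already be filtered by causality. The numerator is cut and the denominator is not. A site that follows the Flow Chart and one that follows the exception would also send different data for the same kind of patient.

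**Working it through.** **1. The plan's own window.** 15 weeks × 7 = 105 days. Protocol and SAP agree, so the mismatch lies between collection and analysis, not between two window lengths.

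**2. Weeks affected per early stopper (g).** The REP runs from the last dose; the exception runs from discontinuation. Doses are due at Weeks 0 and 4, then every 12 weeks.
- Stop registered right after a dose: g = 15 weeks.
- Stop registered at Week 4 after a Week 0 dose: g = 15 − 4 = 11 weeks.
- Stop registered at the next 12-weekly dosing visit: g = 15 − 12 = 3 weeks.

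The working range is 3 to 15 weeks, or 21 to 105 days.

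**3. Share of the patient's own counted exposure.** With the last dose at week L, the SAP counts L + 15 weeks, so the share is g/(L + 15).

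| Last dose | g = 3 | g = 15 |
|---|---|---|
| Week 4 | 3/19 = 16% | 15/19 = 79% |
| Week 28 | 3/43 = 7% | 15/43 = 35% |

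**4. Patient-years across the trial.** The documents give no discontinuation rate. Assume 5% to 10% of 168: 8.4 and 16.8, rounded to 8 and 17 patients.
- Low end: 8 × 21/365.25 = 0.5 patient-years.
- High end: 17 × 105/365.25 = 4.9 patient-years.

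**5. Denominator.** Assume all 168 complete dosing, and use the SAP 11.2.1 exposure definition.
- Risankizumab from Week 0: 112 patients × (40 × 7 + 105) = 112 × 385 days.
- Switched from placebo at Week 16: 56 patients × (24 × 7 + 105) = 56 × 273 days.
- Total: (43,120 + 15,288)/365.25 = 159.9, about 160 patient-years.

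The gap is then 0.5/160 = 0.3% to 4.9/160 = 3.1%. This is slightly generous at the top, because some of the assumed stoppers would be placebo patients who never add risankizumab exposure.

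**6. Cross-check within one risankizumab arm.** With a share d stopping early and completers counted for 40 + 15 = 55 weeks, the under-collected share of person-time is

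d·g / [(1 − d)·55 + d·(L + 15)].

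Over g from 3 to 15 and L from 0 to 28:
- d = 5%: 0.3% to 1.4%.
- d = 10%: 0.6% to 2.9%.
- d = 19%: 1.1% to 6.0%.

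The 19% is an indirect upper guide: protocol 7.7 expects at least 68 of 84 patients (56 + 28) per dose to reach one year, and 1 − 68/84 = 19%.

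For Part A, replacing 55 by 16 weeks and using L = 0 or 4, d = 5% gives 0.9% to 4.7%.

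At a constant event rate these shares approximate the relative under-count of the event types that need not be reported.

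**The case against.** The other side has several good points.

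- **Wording.** The exception does not contain the word *only*, whereas the next bullet, on the period after the end of trial, does. The figure under the AE collection heading is not shown in the copy reviewed and may clarify the periods. A reader might infer that under-counting is certain across the trial. The documents do not support that: some sites may record everything. But the exception is set against the default rule and starts at discontinuation, so the narrowing is its natural sense, and no other text overrides it.
- **Other provisions.** A reader might infer that cancers would be lost. They would not: protocol 5.3.6.1 requires new or worsening cancers to be reported as serious however long after stopping. Protocol 2.3 and 3.1.3 send all observed cardiovascular events to adjudication, but an event that nobody had to report cannot be adjudicated, so here the texts conflict rather than settle the matter. The event that led to stopping is captured, because it precedes the exception.
- **Safety database.** The sample size is set by one-year exposure, so a reader might infer that this central safety dataset is biased. Early stoppers cannot enter the extension and mostly will not reach one year. The problem concerns overall AE counts and rates.
- **Size.** Giving each stopper the full 105 days (2.3 to 4.9 patient-years) is a ceiling. It requires every stop to be registered on the day of the last dose.

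**Conclusion.** The inconsistency is real and should be reconciled. As written, 5.3.6.2 restricts what must be collected from early stoppers while 5.3.6.2 itself, 7.3.4 and SAP 11.2.1 analyse the same weeks as fully observed. Where sites follow the exception, non-serious AEs and unrelated SAEs are under-counted and rates per 100 patient-years are too low.

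The effect is modest: about 0.5 to 4.9 patient-years, roughly 0.3% to 3% of about 160. This assumes that 5% to 10% stop early, that 3 to 15 weeks are affected in each, and that events occur at a constant rate. The documents give neither the discontinuation rate nor the timing of its registration. Part A could be affected proportionally more, since its exposure is shorter.

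A reader might infer that the bias favours risankizumab over placebo. That does not follow: the direction depends on how early stopping differs by arm, which is unknown.

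**What to change.** In protocol 5.3.6.2, state that all AEs, SAEs and AESIs are recorded on the CRF through the REP (last dose plus 15 weeks) for every patient still in contact, including those who stop drug early, and that the limit to related SAEs and related AESIs begins only after the REP ends.

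If the collection rule is to stay as it is, SAP 11.2.1 should end both the treatment-emergent window and the exposure denominator for these patients at the point where full AE collection stops, and the protocol's on-treatment definitions should match.

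The cost of the first option is a short amendment with IRB review and a little more data entry. The visits and AE rows already exist for patients who keep attending. For those with only telephone or vital status contact, AE capture will depend on that contact.
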